### Secondary Endpoints:

- *Determine the mean change in PAPm in both groups on Entresto from week 12 to week 32 in longitudinal study*
  - *Statistical Plan: The changes in PAPm from week 12 to week 32 constitute continuous data. The distribution of average change in PAPm from week 8 to week 32 will be assessed in both group A and B. The distribution of changes in*

PAPm will be assessed for normality. If the distributions are normal, the results will be presented as means with standard errors. If the distributions are not normal, the results will be presented as medians with interquartile ranges.

- *Determine the difference between mean change in PAPm from baseline on ACEI/ARB to 6 weeks on Entresto (Groups A and B)*
  - Statistical Plan: The distribution of the average change in PAPm from baseline to 6 weeks will be assessed in Group A and combined with the distribution of change in PAPm from week 6 to week 12 in Group B. The combined distributions will be assessed for normality. If the combined distribution of changes in PAPm is normal, the results will be presented as means with standard errors. If the distributions are not normal, the results will be presented as medians with interquartile ranges.
  
- *Determine the impact of therapy over time on standard 6 minute walk test, assessing distance walked and changes in PAPm during recovery after the walk.*
  - Statistical Plan: These changes in distance walked from baseline to 6 weeks constitute continuous data. Therefore, the distribution of average changes in PAPm from baseline to 6 weeks will be assessed in Group A and Group B. If both distributions are normal, t-testing will be performed to compare the mean changes between groups. If the distributions are not normal, Wilcoxon testing will be used.  $P < 0.05$  will be significant.

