  - Statistical Plan (*Intensive Phase, patients in both groups as their own control after 6 weeks of Entresto- Group A: week 6 minus baseline; Group B: week 12 minus week 6*): The change in PAPm from pre to peak exercise at baseline and at 5 minute intervals for 30 minutes of recovery will be compared to the change in PAPm from pre to peak exercise and at 5 minute intervals for 30 minutes of recovery at 6 weeks in Group A. If the distributions are normal, the results will be presented as means with standard errors. If the distributions are not normal, the results will be presented as medians with interquartile ranges. The change in PAPm from pre to peak exercise at 6 weeks and at 5 minute intervals for 30 minutes of recovery will be compared to the change in PAPm from pre to peak exercise and at 5 minute intervals for 30 minutes of recovery at week 12 in Group B. If the distributions are normal, the results will be presented as means with standard errors. If the distributions are not normal, the results will be presented as medians with interquartile ranges.

- Statistical Plan (*Intensive Phase, patients on the Entresto Group A: week 6 minus baseline*) compared to patients on continued ACEi/ARB therapy; Group B: week 6 minus baseline): The change in PAPm from pre to peak exercise and at 5 minute intervals for 30 minutes of recovery at 6 weeks in Group A will be compared to the change in PAPm from pre to peak exercise and at 5 minute intervals for 30 minutes of recovery at 6 weeks in Group B. If both distributions are normal, t-testing will be performed to compare the mean changes between groups. If the distributions are not normal, Wilcoxon testing will be used.  $P < 0.05$  will be significant.
- Statistical Plan (*Longitudinal Phase, Patients in both groups - week 32 minus week 12*): The change in PAPm from pre to peak exercise and at 5 minute intervals for 30 minutes of recovery at 32 weeks will be compared to the change in PAPm from pre to peak exercise and at 5 minute intervals for 30 minutes of recovery at 12 weeks in both groups. If the distributions are normal, the results will be presented as means with standard errors. If the distributions are not normal, the results will be presented as medians with interquartile ranges.
- *Determine the impact of therapy over time on standard double Master's step test, assessing changes in PAPm during recovery after the test.*

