  - Statistical Plan (*Intensive Phase, patients in both groups as their own control after 6 weeks of Entresto- Group A: week 6 minus baseline; Group B: week 12 minus week 6*): The change in PAPm, blood pressure and heart rate from pre to peak isometric exercise at baseline and at 5 minute intervals for 15 minutes of recovery will be compared to the changes in PAPm, blood pressure and heart rate from pre to peak isometric exercise and at 5 minute intervals for 15 minutes of recovery at 6 weeks in Group A. If the distributions are normal, the results will be presented as means with standard errors. If the distributions are not normal, the results will be presented as medians with interquartile ranges. The change in PAPm, blood pressure and heart rate from pre to peak isometric exercise at 6 weeks and at 5 minute intervals for 15 minutes of recovery will be compared to the change in PAPm, blood pressure and heart rate from pre to peak isometric exercise and at 5 minute intervals for 15 minutes of recovery at week 12 in Group B. If the distributions are normal, the results will be presented as means with standard errors. If the distributions are not normal, the results will be presented as medians with interquartile ranges.
  - Statistical Plan (*Intensive Phase, patients on the Entresto Group A: week 6 minus baseline) compared to patients on continued ACEi/ARB therapy; Group B: week 6 minus baseline*): The change in PAPm, blood pressure and heart rate from pre to peak isometric exercise and at 5 minute intervals for 15 minutes of recovery at 6 weeks in Group A will be compared to the change in PAPm, blood pressure and heart rate from pre to peak isometric exercise and at 5 minute intervals for 15 minutes of recovery at 6 weeks in Group B. If both distributions are normal, t-testing will be performed to compare the mean changes between groups. If the distributions are not normal, Wilcoxon testing will be used.  $P < 0.05$  will be significant.
  - Statistical Plan (*Longitudinal Phase, Patients in both groups - week 32 minus week 12*): The change in PAPm, blood pressure and heart rate from pre to peak

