  - *Statistical Plan (Intensive Phase, patients on the Entresto Group A: week 6 minus baseline) compared to patients on continued ACEi/ARB therapy; Group B: week 6 minus baseline):* The change in PAPm, blood pressure and heart rate during Stroop Color test and at 5 minute intervals for 15 minutes of recovery at 6 weeks in Group A will be compared to the change in PAPm, blood pressure and heart rate during Stroop Color test and at 5 minute intervals for 15 minutes of recovery at 6 weeks in Group B. If both distributions are normal, t-testing will be performed to compare the mean changes between groups. If the distributions are not normal, Wilcoxon testing will be used.  $P < 0.05$  will be significant.
  - *Statistical Plan (Longitudinal Phase, Patients in both groups - week 32 minus week 12):* The change in PAPm, blood pressure and heart rate during Stroop Color test and at 5 minute intervals for 15 minutes of recovery at 32 weeks will be compared to the change in PAPm, blood pressure and heart rate during Stroop Color test and at 5 minute intervals for 15 minutes of recovery at 12 weeks in both groups. If the distributions are normal, the results will be presented as means with

standard errors. If the distributions are not normal, the results will be presented as medians with interquartile ranges.

- *Determine the change in NT-proBNP and the BNP/NT-proBNP ratio*
  - Statistical Plan (*Intensive Phase, patients in both groups as their own control - Group A: week 4 minus baseline; Group B: week 8 minus week 4*) The change in NT-proBNP from baseline to week 6 will be assessed in Group A and combined with the change in NT-proBNP levels from week 6 to week 12 in Group B. These distributions will be continuous distributions. If the distributions are normal, the results will be presented as means with standard errors. If the distributions are not normal, the results will be presented as medians with interquartile ranges.
  - Statistical (*Intensive Phase, patients on the Entresto Group A: week 6 minus baseline) compared to patients on continued ACEi/ARB therapy; Group B: week 6 minus baseline*): The change in NT-proBNP levels will be assessed from baseline to week 6 in Group A and Group B. If both distributions are normal, t-testing will be performed to compare the mean changes between groups. If the distributions are not normal, Wilcoxon testing will be used.  $P < 0.05$  will be significant.

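### The week-6 Group A versus Group B plans for the walk, step, handgrip and Stroop tests contradict themselves: headings say week 6 minus baseline, text compares week-6 responses only

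*Combined protocol and SAP*

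**What the plan says.** All references are to the combined protocol and SAP, section VI, Statistical Analysis, Secondary Endpoints, unless stated otherwise.

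- **Heading.** For all four tests the between-group plan for the intensive phase gives Group A as week 6 minus baseline, "compared to patients on continued ACEi/ARB therapy; Group B: week 6 minus baseline".
- **Text, walk and step tests.** The comparison is of the pre-to-peak and recovery PAPm response "for 30 minutes of recovery at 6 weeks in Group A will be compared to the change in PAPm from pre to peak exercise" and recovery at 6 weeks in Group B.
- **Text, handgrip and Stroop tests.** The same construction: "for 15 minutes of recovery at 6 weeks in Group A will be compared to the change in PAPm, blood pressure and heart rate", again at 6 weeks in Group B.
- **Test.** Each entry then calls for a t-test of mean changes between groups, or a Wilcoxon test if the distributions are not normal, at P < 0.05.
- **Walk, separate entry.** The walk section opens with a plan that begins "These changes in distance walked from baseline to 6 weeks constitute continuous data". It then refers to PAPm changes from baseline to 6 weeks in Groups A and B, without naming peak or recovery points.
- **Data.** All four tests are done at baseline and at week 6 (section V.a, visit schedule; section V.e, baseline variables).

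**The concern.** The heading subtracts a baseline visit that the sentence beneath it never mentions. The only change the sentence defines is within one visit: from before the test to peak, during the test, or recovery. The heading therefore describes a difference of differences, and the text a single difference at week 6. From the same data these give different estimates and P values.

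Each entry declares a significance threshold. If the conflict stays, the choice between two eligible tests for each outcome would be made after the data are in, in a trial whose physicians are not blinded (II. Study Design). On the literal text, Group B's baseline test responses would also enter none of the headed analyses of these tests, because Group B's own-control contrast is "Group B: week 12 minus week 6".

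**Working it through.** **1. Is the week-6-only sentence just shorthand?** Compare it with its neighbours:

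| Entry | Visits in heading | Visits in text |
|---|---|---|
| Own-control, four tests | A: baseline, 6; B: 6, 12 | the same |
| Longitudinal, four tests | 12, 32 | the same |
| A v B, NT-proBNP and diuretic dose | baseline, 6 | the same |
| A v B, four tests | baseline, 6 | 6 only |

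The walk and step own-control plans name the baseline test in so many words: "The change in PAPm from pre to peak exercise at baseline and at 5 minute intervals for 30 minutes of recovery will be compared". The NT-proBNP plan, under the same between-group heading, says "The change in NT-proBNP levels will be assessed from baseline to week 6 in Group A and Group B". Where baseline is meant, the text elsewhere says so. The conflict is real and occurs four times.

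**2. The plan's own figure.** The Power Analysis covers only PAPm change at 6 weeks: 10 per group, 20% of 25 = 5 mm Hg, SD 3.4. SE = 3.4 × √(2/10) = 1.52; 5/1.52 − 1.96 = 1.33; power 90.8% by the normal approximation (87.5% by noncentral t), against the stated 90%. No SD, correlation or power is given for any test response, so this figure cannot size the present point. The steps below use SD units and an assumed correlation r between a patient's baseline and week-6 responses, with equal SDs at the two visits.

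**3. Gap between the two readings.** Let D0 and D6 be the A − B differences in mean response at baseline and at week 6.

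- Text: D6.
- Heading: D6 − D0.
- Gap: D0, with SE = SD × √(1/10 + 1/10) = 0.447 SD.
- The chance that D0 exceeds 0.5 SD in either direction is 2 × [1 − Φ(0.5/0.447)] = 26%.

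**4. Precision relative to week-6-only.**

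- Change score: variance ratio 2(1 − r).
- Covariate adjustment (ANCOVA): (1 − r²) × (1 + 1/16). The second factor allows for estimating the slope: 1 + 1/(2n − 4), n = 10.

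| Assumed r | Change score | ANCOVA | Patients ANCOVA is worth |
|---|---|---|---|
| 0.3 | 1.40 | 0.91 × 1.0625 = 0.97 | about 3% more |
| 0.5 | 1.00 | 0.75 × 1.0625 = 0.80 | about 25% more |
| 0.7 | 0.60 | 0.51 × 1.0625 = 0.54 | about 85% more |
| 0.9 | 0.20 | 0.19 × 1.0625 = 0.20 | about 5 times as many |

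Break-even for ANCOVA: (1 − r²) × 17/16 = 1, so r² = 1/17 and r = 0.24. Break-even for the change score: 2(1 − r) = 1, so r = 0.5.

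**The case against.** **Baseline is not clearly discarded.** The heading is part of the plan, and the t-test sentence speaks of mean changes between groups. Heading and text can be read together, with the heading supplying the visits and the sentence the variable. This stands, and it is why the point is a contradiction rather than a decision to drop baseline. A reader might infer that the baseline test is thrown away, but the documents do not support that: Group A's baseline test is used in the own-control analyses. They do not support the opposite either, because the only change the sentence defines is within-test. The footnote to the endpoints, which describes Group A compared with B at 6 weeks, fits both readings.

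**The walk has its own baseline-to-week-6 entry.** True, but it starts from distance walked, moves to PAPm without peak or recovery points, and says nothing about the other three tests. It does not resolve the headed walk plan.

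**Randomization makes week-6-only valid.** This stands in full. The comparison is unbiased in expectation, and its standard error already includes chance baseline imbalance, so the error rate stays nominal. A reader might infer that chance imbalance would be reported as a drug effect in some systematic way; that is not so.

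**The precision argument is partly a preference.** Neither heading nor text proposes covariate adjustment, and the heading's change score is no better than week-6-only at r = 0.5 and 40% worse in variance at r = 0.3. This stands. The gain claimed here is for ANCOVA only.

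**The stakes are small.** These are secondary endpoints in a 20-patient pilot, and the week-6 co-primary already uses change from baseline. This also stands.

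**Conclusion.** The four between-group plans contradict their own headings and should be reconciled before analysis. The established defect is an undefined analysis, not bias.

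The two readings differ by the observed baseline difference between arms, with SE 0.45 SD at 10 per arm. It is tempting to turn this into mm Hg and set it against the 5 mm Hg planning effect. At an assumed SD of 5 (range 4 to 6), the SE is 2.2 (1.8 to 2.7) and the 95% limit 4.4 (3.5 to 5.3). That comparison is not supported: the SD is not in the documents, 4.4 is a 95% limit rather than a typical gap (the median is about 0.674 × 2.24 = 1.5), and the 5 mm Hg belongs to PAPm change at 6 weeks, not to a within-test response.

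Under the assumed correlations of 0.5 and 0.7, baseline adjustment is worth about 25% and 85% more patients than week-6-only, and it gains above about 0.24. The contradiction itself depends on none of these assumptions. It merits correction because the correction is nearly free; neither co-primary endpoint is affected.

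**What to change.** In the four entries, replace both the comparison sentence and the t-test/Wilcoxon sentences, since those tests take no covariate, by:

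*For each measured variable and time point (peak or during-test, and each recovery time), the week-6 within-test response will be compared between Group A and Group B by ANCOVA with the patient's baseline-visit response for the same test, variable and time point as covariate; if residuals are clearly non-normal, a rank-based ANCOVA will be used.*

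Change the four headings to match.

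The minimum alternative is to make the text follow the heading and compare week 6 minus baseline between groups. That removes the contradiction but does not guarantee a gain in precision.

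Cost: SAP wording in four entries, no new visits or tests, and one degree of freedom per ANCOVA (17 residual instead of 18).

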## Power Analysis

There will be 20 patients total, 10 in each group.

*Between group comparison:* This sample size will provide 90% power with 2-sided alpha of 0.05 to detect a 20% difference between the 2 groups (Entresto and ACEI/ARB) in the PAPm change at 6 weeks, based on an assumed baseline PAPm of 25 mm, using a t-test with a standard deviation in the mean change of as high as 3.4. We do not yet have data on which to estimate the standard deviation of this change, but we have found a standard deviation of 3-4 mm Hg of PAPm pressures during 5 day periods in stable patients followed on Cardiomems devices at Brigham and Women's Hospital (unpublished data).

*All patients after 6 weeks of Entresto compared to chronic ACEI/ARB at baseline:* There is additional power for this highest secondary endpoint. Assuming the PAPm baseline on ACEI/ARB mean of 25mm, a sample size of 20 patients will provide 90% power with two-sided alpha of 0.05 paired t-test to detect a 20% decrease (to PAPm of 20 mm) after 6 weeks of Entresto, with a standard deviation for the change as high as 6.8.

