## Statistical Analysis

### Co-Primary Endpoints:

#### *Intensive Phase:*

- *Determine the difference between mean change in mean pulmonary artery pressure (PAPm) after 6 weeks on Entresto compared to 6 weeks on continued ACEi/ARB*
  - *Statistical Plan: These changes from baseline to 6 weeks constitute continuous data. Therefore, the distribution of average changes in PAPm from baseline to 6 weeks will be assessed in Group A and Group B. If both distributions are normal, t-testing will be performed to compare the mean changes between groups. If the distributions are not normal, Wilcoxon testing will be used. P <0.05 will be significant.*

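### The t-tests named in the Power Analysis give 87.5% and 87.7% power at the plan's own inputs, not 90%; 90% holds only for SDs up to 3.26 and 6.54 mm Hg, not 3.4 and 6.8

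*Combined protocol and SAP*

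**What the plan says.** The Power Analysis section of the combined protocol and SAP fixes the sample at 20 patients, 10 per group, and makes two power claims.

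- **Between groups, change in PAPm at 6 weeks (co-primary).** "This sample size will provide 90% power with 2-sided alpha of 0.05 to detect a 20% difference between the 2 groups", at an assumed baseline PAPm of 25 mm Hg, "using a t-test with a standard deviation in the mean change of as high as 3.4".
- **All patients, baseline on ACEi/ARB against 6 weeks of Entresto (secondary).** The section introduces this with "There is additional power for this highest secondary endpoint" and continues: "a sample size of 20 patients will provide 90% power with two-sided alpha of 0.05 paired t-test to detect a 20% decrease", from 25 to 20 mm Hg, "with a standard deviation for the change as high as 6.8".

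The same section says that no data yet exist on the SD of the change. The only empirical figure it offers is of another kind: "we have found a standard deviation of 3-4 mm Hg of PAPm pressures during 5 day periods in stable patients".

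The Statistical Analysis section (Co-Primary Endpoints, Intensive Phase) agrees on the primary test. If the changes are normally distributed in both groups, "t-testing will be performed to compare the mean changes between groups"; otherwise a Wilcoxon test is used.

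**The concern.** Both claims name a t-test and give an SD as a ceiling, so each can be checked exactly. With 18 or 19 degrees of freedom, a t-test has visibly less power than a large-sample normal formula suggests. If the figures come from that formula, 90% is not reached at the stated ceilings.

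The type II error would then be about 12.5% and 12.3% rather than 10%. The ceiling also matters more than usual here: because the plan has no estimate of the SD of the change, the tolerated SD is the main thing a reader can use to judge whether 20 patients are enough.

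**Working it through.** **Inputs, all from Power Analysis.** Two-sided alpha 0.05; 10 per group, or 20 paired; SD of the change 3.4 (two-sample) or 6.8 (paired). The difference is 0.20 × 25 = 5 mm Hg. Reading the 20% as a share of the baseline is an interpretation, but the paired claim, which describes a fall from 25 to 20 mm Hg, supports it.

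**Step 1. Noncentrality.**

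- Two-sample: 5 / (3.4 × √(2/10)) = 5 / 1.5205 = 3.288, with 18 df.
- Paired: 5 / (6.8 / √20) = 5 / 1.5205 = 3.288, with 19 df.

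The two claims share one noncentrality and differ only by one degree of freedom.

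**Step 2. Reproduce the plan's figure with the normal approximation.** Power = Φ(3.288 − 1.960) = Φ(1.328) = 90.8% for both. The largest SDs that keep 90% under this formula are:

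- two-sample: 5 / [(1.960 + 1.282) × √(2/10)] = 3.449;
- paired: 5 × √20 / (1.960 + 1.282) = 6.898.

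Cut to one decimal, these are the plan's 3.4 and 6.8. The sample sizes also match: 2 × [(1.960 + 1.282) × 3.4 / 5]² = 9.7, so 10 per group, and [(1.960 + 1.282) × 6.8 / 5]² = 19.4, so 20 patients.

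**Step 3. Exact power of the named tests.** Power = P(|T| > critical value), where T is noncentral t with noncentrality 3.288.

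| | Two-sample | Paired |
|---|---|---|
| Degrees of freedom | 18 | 19 |
| Critical value | 2.101 | 2.093 |
| Power at the stated SD | 87.5% | 87.7% |
| Type II error | 12.5% | 12.3% |
| Largest SD for 90% power | 3.26 | 6.54 |
| Stated SD / largest SD | 3.4 / 3.26 = 1.04 | 6.8 / 6.54 = 1.04 |
| Difference detectable with 90% power at the stated SD | 5.2 mm Hg | 5.2 mm Hg |

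A simulation of 400,000 normal data sets per case gives the same 87.5% and 87.7%.

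**Step 4. What would restore 90%.**

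- At the stated SDs: 11 per group (90.6%) for the primary. For the paired test, 21 patients give 89.3% and 22 give 90.8%.
- At the planned size: an SD of 3.2 gives 91.0% for the primary (3.3 gives 89.3%), and 6.5 gives 90.3% for the paired test (6.6 gives 89.5%).

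**Step 5. Scale against the uncertainty in the SD.** Exact primary power is 94% at an SD of 3.0, 87% at 3.4 and 75% at 4.0. These values are only an illustration, because the plan's 3-4 mm Hg describes pressures within 5-day periods and not the 6-week change.

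**The case against.** The best defence is that the figures are not arbitrary. One standard formula, the two-sided normal approximation, reproduces both 90% claims, both SD ceilings and both sample sizes, so no input is wrong. The shortfall is 2.5 and 2.3 points, 0.2 mm Hg in detectable difference, or two patients in a trial labelled a pilot. The true SD is unknown, as the plan openly says, and moving it from 3.0 to 4.0 changes power by 19 points, which dwarfs the correction.

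Most of this stands, and it is why the point is minor. It does not rescue the figures. The plan names a t-test and a paired t-test, not an approximation, and 87.5% does not round to 90%. A ceiling expressed as the highest tolerable SD is right or wrong whatever the true SD turns out to be. Uncertainty about the SD is a reason to state the ceiling correctly.

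**Conclusion.** Both power statements are wrong as written. Under the tests the plan names, power is 87.5% for the primary comparison and 87.7% for the paired secondary one, and the SD ceilings for 90% are 3.26 and 6.54. The stated power is 2.5 and 2.3 points too high, and the stated ceilings about 4% too high. Severity is minor: the design and the planned 20 patients can stay.

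The result assumes normally distributed changes, equal SDs in the two groups, complete data on all 20 patients, and a 20% effect meaning 5 mm Hg. That a normal approximation was used is an inference, since the plan names no formula or software; the conclusion does not depend on it.

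A side point carries no weight in this verdict. In the Statistical Analysis section, the plan for the secondary endpoint ("Determine the difference between mean change in PAPm from baseline on ACEI/ARB to 6 weeks on Entresto (Groups A and B") is descriptive only: mean with standard error, or median with interquartile range. The paired t-test appears only in Power Analysis.

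**What to change.** Keep 20 patients and correct Power Analysis in one of two ways.

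- **Restate the power.** Ten per group gives about 87% power (two-sample t-test, two-sided 0.05) for a 5 mm Hg difference at an SD of the change of 3.4; 20 patients give about 88% power (paired t-test) for a 5 mm Hg decrease at an SD of 6.8.
- **Keep 90% and lower the ceilings** to 3.2 for the between-group comparison and 6.5 for the paired one.

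In either case, write the effect as 5 mm Hg and name the formula or software. It would also help to show primary power at SDs of 3.0, 3.4 and 4.0 (94%, 87%, 75%), labelled as illustration.

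Separately, add the paired t-test to the analysis of the baseline-to-6-weeks secondary endpoint, or remove its power claim.

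The cost is wording only: no added patients, visits or data. The one drawback is a slightly less favourable stated power or SD tolerance.
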